Test Device	Vessix Renal Denervation System: 
 • Vessix Reduce™ Catheter (4.0, 5.0, 6.0 and 7.0 mm) • Vessix™ Generator (bipolar radio frequency)
Control Therapy	Masked procedure (renal angiogram)
Device Sizes	The Vessix Reduce Catheter is available in balloon diameters of 4.0 mm, 5.0 mm, 6.0 mm and 7.0 mm with a balloon length of 25 mm and a total catheter working length of approximately 90 cm. The number of electrodes on each balloon varies from 4 to 6 bipolar electrodes, depending on balloon diameter. The catheter is compatible with a 7F guide sheath.
Study Design	Prospective, multicenter, single blinded, randomized, controlled, pilot study
Planned Number of Subjects	Up to 100 randomized subjects
Planned Number of Centers / Countries	Up to 20 centers in the US
Primary Efficacy Assessment	Mean reduction in average 24-hour ambulatory systolic blood pressure (ASBP) at 8 weeks post randomization Due to enrollment termination (51 subjects randomized), the primary efficacy statistical hypothesis testing will not be conducted. All assessments will be observational.
Safety Assessments	Safety Assessments analyzed at all follow-up time points: 
 • All-cause death • Renal failure • Hospitalization for hypertensive crisis • Hospitalization due to severe hypotension/syncope

REDUCE-HTN: REINFORCE	
	
Safety Assessments analyzed at 4 weeks:
 
 • Significant embolic event resulting in end-organ damage or intervention to prevent it • Renal artery dissection or perforation requiring intervention • Vascular complications requiring surgical repair, interventional procedure, thrombin injection, or blood transfusion 
Safety Assessments analyzed at 6 months:
 
 • Significant new renal artery stenosis assessed by duplex ultrasound (DUS) and confirmed by the angiographic core laboratory [$>70\%$ stenosis by computed tomographic angiography (CTA) or digital subtraction angiography (DSA)] through 6 months post randomization 
Note: All Safety Assessments will be adjudicated by an independent Clinical Events Committee (CEC).

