12.5.1. Diagnostic Renal Angiogram, Masked Procedure and Renal Denervation Procedure

Patients meeting all clinical eligibility and anatomic eligibility based on non-invasive imaging will undergo diagnostic renal angiography. If anatomic eligibility is confirmed during the diagnostic angiogram, the patient will be immediately randomized and enrolled to the control or to the renal denervation treatment.

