12.5.1.1. Diagnostic Renal Angiogram

A diagnostic aortogram should be performed to obtain visual confirmation of all renal arteries. A selective arteriogram will be performed on each renal artery using a diagnostic catheter in order to confirm anatomic eligibility is met.

NOTE: If new anatomical exclusion criteria are identified during the angiogram the patient should not be randomized.

Upon catheter/sheath removal, either manual compression or commercialized closure devices can be used to achieve hemostasis at the puncture site. Standard-of-care post-intervention monitoring procedures should be followed.

Angiographic images must be sent to the angiographic core laboratory for evaluation.

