12.5.1.2. Masked Procedure

The masked procedure will consist of the diagnostic renal angiogram performed to confirm anatomic eligibility (see Section 12.5.1.1).

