14.2. General Statistical Methods

14.2.1. Analysis Sets

The primary and pre-specified additional assessments will be analyzed on an intent-to-treat (ITT) basis and on a per-protocol basis. For the ITT analysis, all subjects who sign the written ICF and are randomized in the study will be included in the analysis population, regardless of whether the subjects receive the assigned treatment. For the per-protocol analysis, only randomized subjects who meet the eligibility criteria and receive the assigned treatment will be included in the analysis population.

The ITT population will be the primary analysis set for the purpose of assessing superiority of Test to Control for 8-week average 24-hour ASBP reduction. All other endpoint analyses will be based on ITT population.

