	
 • Renal disorders (advanced chronic kidney disease, renal artery stenosis, polycystic kidney(s), urinary tract infection, hematuria, analgesic abuse) • Endocrine disorders (pheochromocytoma, hyperaldosteronism, Cushing’s syndrome, acromegaly, hyperparathyroidism, hyperthyroidism or hypothyroidism) • Drug/Substance Intake such as certain antidepressants, carbenoxolone (UK), cyclosporine, erythropoietin, hormonal contraceptives, buspirone, carbamazepine, bromocriptine, clozapine, estrogens, NSAIDS, ethanol, nasal decongestants with adrenergic effects, MAOIs, adrenoceptor stimulants, gluco- and mineralocorticosteroids, nicotine use, cocaine, amphetamines, and black liquorice when consumed in excess • Other causes such as neurological disorders, obstructive sleep apnea, scleroderma, neurofibromatosis, pregnancy, cancers, aortic coarctation, bradycardia or ischemia
Hypertensive Crisis	
Hypertensive crisis includes hypertensive emergencies and hypertensive urgencies.
 
Hypertensive emergencies are characterized by severe elevations in BP (180/120 mm Hg) complicated by evidence of impending or progressive target organ dysfunction.²⁶ They require immediate BP reduction (not necessarily to normal) to prevent or limit target organ damage. Examples include hypertensive encephalopathy, intracerebral hemorrhage, acute myocardial infarction, acute left ventricular failure with pulmonary edema or unstable angina pectoris.
 
Hypertensive urgencies are those situations associated with severe elevations in BP without progressive target organ dysfunction.
 
NOTE: See Major Adverse Event definition.

Investigational Devices	
Vessix Renal Denervation System
 
 • Vessix Reduce Catheter (4.0, 5.0, 6.0 and 7.0 mm) • Vessix Generator (bipolar radio frequency)
Major Adverse Event	
Through 4 weeks post randomization:
 
 • All-cause death • Renal failure

Table 27.2-1: Definitions

Term	Definition
	
 • Hospitalization for hypertensive crisis • Hospitalization due to severe hypotension/syncope • Significant embolic event resulting in end-organ damage or intervention to prevent it • Renal artery dissection or perforation requiring intervention • Vascular complications requiring surgical repair, interventional procedure, thrombin injection, or blood transfusion

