Source Data	
All information in original records of clinical findings, observation or other activities in a clinical investigation necessary for the reconstruction and evaluation of the clinical investigation

Source Document	
Printed, optical or electronic document containing source data. Examples: Hospital records, laboratory notes, device accountability records, photographic negatives, radiographs, records kept at the investigation site, at the laboratories and at the medico-technical departments involved in the clinical investigation

Stroke	
A new focal neurological deficit or loss of brain function with presumed vascular origin persisting more than 24 hours and with a neuro-imaging study that does not indicate a different etiology. The 24-hour criterion is not applicable if the subject undergoes cerebrovascular surgery or expires secondary to a stroke within the first 24 hours following the onset of the symptoms. It includes subjects presenting with clinical signs and symptoms suggestive of subarachnoid hemorrhage, intracerebral hemorrhage, or cerebral infarction. It does not include stroke events in cases of

Table 27.2-1: Definitions

Term	Definition
	blood disorders such as leukemia and excludes subjects with a history of stroke secondary to trauma.
Target Blood Pressure	OSBP <140mmHg
Vascular Complications	Clinically significant groin hematoma, arteriovenous fistula, pseudoaneurysm, or excessive bleeding requiring surgical repair, interventional procedure, thrombin injection, or blood transfusion (requiring more than 2 units of packed red blood cells within any 24 hour period during the first 7 days post-renal denervation treatment).

NOTE: See Major Adverse Event definition.

Abbreviations are defined in Table 27.1-1.

28. Bibliography

- ¹ Levey AS, Coresh J, Greene T, et al. Chronic Kidney Disease Epidemiology Collaboration. Using standardized serum creatinine values in the modification of diet in renal disease study equation for estimating glomerular filtration rate. *Ann Intern Med.* 2006;145(4):247-54.
- ² Gewirtz JR, Bisognano JD. Catheter-based renal sympathetic denervation: A targeted approach to resistant hypertension. *Cardiology Journal.* 2011;18(1):97-102.
- ³ Uder M, Schmid A, Titze S, et al. Renal artery denervation for the treatment of hypertension: Opening up new horizons. *CardioVascular and Interventional Radiology.* 2011;34(3):442-444.

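### The transfusion limb of Vascular Complications is dated from renal denervation, so read literally no Control subject can meet it

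*Combined protocol and SAP*

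**What the plan says.** Section 8.2 and the synopsis list this 4-week safety assessment without limiting it to one arm: "Vascular complications requiring surgical repair, interventional procedure, thrombin injection, or blood transfusion". The Major Adverse Event entry in Table 27.2-1 repeats the item under the time frame "Through 4 weeks post randomization".

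The Vascular Complications entry in the same table names four qualifying interventions: surgical repair, an interventional procedure, thrombin injection and transfusion. Only transfusion carries a further condition in parentheses: "requiring more than 2 units of packed red blood cells within any 24 hour period during the first 7 days post-renal denervation treatment". The entry then refers the reader to the Major Adverse Event definition.

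On what Controls undergo, Section 12.5.1.2 says: "The masked procedure will consist of the diagnostic renal angiogram performed to confirm anatomic eligibility". Section 12.5.1.1 describes the end of that angiogram, where "either manual compression or commercialized closure devices can be used to achieve hemostasis at the puncture site".

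Section 14.2.1 includes every consented and randomized subject in the intention-to-treat (ITT) set, "regardless of whether the subjects receive the assigned treatment", and adds: "All other endpoint analyses will be based on ITT population". Section 14.3 allows Test-Control differences with 95% confidence intervals to be presented as needed.

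**The concern.** An event definition used in a randomized comparison needs a start date that every subject has. Here the seven-day clock for transfusion starts at a treatment that only one arm is assigned. The risk it captures, bleeding at the arterial access site, is present in both arms because the Control procedure also involves a puncture.

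If the rule is applied as written, a Test subject with an access-site bleed and a qualifying transfusion is counted. A Control with the same bleed and the same transfusion is not, unless one of the other three interventions was also needed. The arms would then be counted by different rules on this limb, and a displayed difference in vascular complications would partly reflect the definition.

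**Working it through.** The plan gives no figure to reproduce, and the point does not rest on a sample size, an error rate or an event count. The check sets the passages side by side.

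**1. Does every subject have the anchor?** Section 12.5 assigns denervation to the treatment group and the masked procedure to the control group. Section 12.5.1.2 makes the masked procedure the angiogram alone. A Control therefore has no denervation date, and neither does a Test subject who was randomized but not denervated.

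**2. Are those subjects in the analysis?** Section 8 places the safety assessments under its Endpoints heading. Section 14.2.1 puts endpoint analyses other than the primary on the ITT population, whether or not the assigned treatment was given. So they are.

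**3. Can they have the event?** Section 12.5.1.1 provides for catheter or sheath removal and hemostasis after the angiogram, so an access-site bleed is possible in a Control.

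**4. Is a restriction to denervated subjects intended?** Where the protocol means such a restriction, it says so. Section 12.11 exempts Controls from the 6-month duplex ultrasound, and Section 15.3.1 limits the 24-month scan to denervated subjects. Nothing comparable is said about vascular complications.

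**5. Result by limb, on the literal reading:**

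| Limb | Test, denervated | Test, not denervated | Control |
|---|---|---|---|
| Surgical repair | can count | can count | can count |
| Interventional procedure | can count | can count | can count |
| Thrombin injection | can count | can count | can count |
| Transfusion | can count | no start date | no start date |

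One limb of four is affected.

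**6. Which anchor is available to all?** Randomization. The Major Adverse Event entry already counts from it. Section 12.5.1 says that once the angiogram confirms eligibility, "the patient will be immediately randomized and enrolled to the control or to the renal denervation treatment". The diagnostic puncture therefore comes just before randomization. Taking the day of randomization as day 0 keeps a bleed from that puncture inside the window.

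**7. Scale.** The documents give no event rate, so neither the number of affected events nor a bias can be derived. As an illustration only: 51 subjects at an exact 2:1 split give 51/3 = 17 Controls, and one uncounted Control event would then lower the displayed Control rate by 1/17 = 5.9 percentage points. The actual split is not stated. Assuming 15 to 20 Controls, the figure runs from 1/15 = 6.7 to 1/20 = 5.0 points. This is the weight of a single event, not an estimate that any event was missed.

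**The case against.** The strongest reply is that the phrase loosely means the index procedure in both arms. Some wording leans that way. The entry refers to the Major Adverse Event definition, which runs from randomization. Section 11.4 uses the idea of assigned treatment for both procedures, and Table 12.1-1 gives the two procedures a single column. On that reading the arms are counted alike. It remains open but is not stated, and Sections 12.11 and 15.3.1 use the same term literally. In addition, Sections 14.2.3 and 24.3 leave adjudication to the CEC Charter, which was not available and may already hold an arm-neutral rule. Both points limit what can be said about the consequence. Neither repairs the protocol text.

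It is also fair that little hangs on this. The synopsis makes all assessments observational, with descriptive analysis for data review. Section 14.3 presents differences only as needed. A transfused bleed would still be reported as an adverse or serious adverse event (Section 22.3), seen by the Data Monitoring Committee (Section 24.2) and open to CEC review (Section 24.3). All of this stands and keeps the point minor. These safeguards protect subjects, but they do not make the adjudicated counts comparable.

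A reader might go further in two ways that the documents do not support:

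- **Controls fall under a looser rule** (any transfusion through 4 weeks), so the direction of bias is open. The parenthesis directly qualifies transfusion, and nothing points to a separate unqualified rule for Controls.
- **The unit threshold and seven-day limit contradict the 4-week listing.** A definitions table may narrow a listed term, so the difference is not in itself an error.

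**Conclusion.** The point holds as a minor defect in a definition. Read literally, the transfusion limb can be met only by denervated subjects, while the assessment is listed for, and analysed in, everyone randomized. If the literal rule was applied, any bias would be under-counting of Control events, and the size cannot be estimated.

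Confidence is high that the wording has this gap. It is lower that any count was affected, since that depends on the CEC having applied the literal rule and on such an event having occurred in a Control, and the documents show neither. The text does not support a conclusion that the safety comparison is in fact biased.

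**What to change.** In the Vascular Complications entry of Table 27.2-1, replace the reference to renal denervation treatment with *post randomization*, stating that the day of randomization is day 0. If the CEC Charter already has an arm-neutral anchor, copy that in instead. Apply the same anchor to both arms when the adjudicated events are tabulated. The unit threshold and window length are for the sponsor and need not change for this purpose.

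The cost is one phrase, amendment approvals under Section 16 if required, and a check of any transfused access-site complication already reported among the 51 subjects. No new visits or tests are needed. The check need not be presented as blind to arm: Section 12.11 provides for unblinding after the 6-month assessments, and under Section 24.3 event dossiers may include source documents, which could show the procedure performed.
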